PSA Suppression with Normal Testosterone Levels: In BCR prostate cancer patients, minimizing toxicity while preserving clinical efficacy is a central goal of treatment. Much of the toxicity of ADT results from its induction of a hypogonadal state. Treatment alternatives to continuous ADT, such as IADT, seek to minimize decrements in quality of life and metabolic parameters induced by medical castration by increasing the percentage of time that patients spend in a eugonadal state. Thus, preservation of, or a return to, normal testosterone level, while maintaining a durable effect on serum PSA, is a potentially clinically relevant endpoint that could be measured utilizing the proposed study design, which incorporates intermittent therapy. In the proposed trial, this is an exploratory endpoint, since cessation of therapy does not necessarily equate to a return to eugonadal state, and there is a considerable variability in the time to serum testosterone recovery in prior studies of short-term ADT or IADT. For example, in a randomized trial of IADT with 6 months of induction ADT followed by randomization to either thalidomide vs. placebo, Gulley and colleagues demonstrated that the median time to low testosterone (defined as > 50 , but < 212 ng/dL) or normal testosterone (defined as > 212 ng/dL) recovery was 12.9 and 16.6 weeks, respectively [54]. However, there was considerable variability with some patients taking up to 40 weeks to achieve a testosterone level > 50 ng/dL. Advanced age and low baseline serum testosterone level (< 212 ng/dL) were associated with a delay in time to testosterone recovery in this study. Twenty percent of men older than 66 years did not achieve normal testosterone levels by 44 weeks after cessation of ADT. In another report by Pickles and colleagues, in 267 patients treated with ADT for 3 months to 3 years in duration, the median time to testosterone recovery after cessation of ADT (defined as testosterone > 10 nmol/L or 288 ng/dL) was approximately 10 months [55]. Again there was considerable variability in the time to recovery; both older age and low baseline serum testosterone were associated with a longer time to testosterone recovery. Despite these limitations, assessment of serum testosterone recovery is an important parameter to be measured in studies of BCR men

receiving novel treatments or treatment strategies that incorporate ADT into the study treatment plan.

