5. EFFICACY

This section outlines the planned analyses of the primary, secondary, and other efficacy endpoints of the study.

Efficacy analyses will be performed in the ITT population, incorporating the randomization stratification factors. All continuous variables will be summarized using number of subjects (n), mean, standard deviation (SD), median, minimum, and maximum. Categorical variables will be summarized with count and percentage.

Time-to-event endpoints will be summarized using the Kaplan-Meier method [6] and displayed graphically where appropriate. Median event times and two-sided 95% confidence interval (CI) for each treatment group will be provided. Stratified Cox proportional-hazard models will be used to estimate the hazard ratio (HR) and its 95% CI. The stratification factors to be used in the analysis are PSADT (< 6 months vs. 6-12 months), and age at study entry (≤ 70 years vs. > 70 years).

The testing for the time-to-event endpoints will be based on the stratified log rank test; non-stratified log rank test will be performed as a sensitivity analysis, as appropriate. Multivariate Cox regression analysis, adjusting for important selected prognostic factors.

The proportional hazard assumption will be assessed graphically by plotting log (-log [estimated survival distribution function]) against log (survival time). The resulting graphs should have approximately parallel lines when the assumption holds. If the proportional hazards assumption is reasonably met, then the HR will be used as an estimate of treatment effect. If the proportional hazards assumption is violated, then the inference remains statistically valid for testing equality in survival distributions, but treatment effect will only be estimated using the median time to event in each treatment group.

Endpoints with binary outcome will be summarized by descriptive statistics (count and percentage) by the treatment group. The risk ratio or risk difference (treatment: control) will be reported along with the corresponding two-sided 95% CI. The two treatment groups will be compared by using the chi-square test; Fisher's exact test may be used if the expected counts in some of the cells are less than 5.

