5.3 Secondary Endpoints

The following secondary endpoints will be analyzed:

A) Quality of Life:

- Mean change from baseline in total FACT-P score over time
- Mean change from baseline in EORTC QLQ-C30/PR25 score over time
- Mean change from baseline in SHIM score over time

B) PSA Modulation:

- Time to PSA progression, which is defined as a rise to greater than 50% of the baseline serum PSA or rise of 2 ng/mL or more above the nadir, whichever is higher, confirmed by repeat measurement at least 2 weeks later (see Table 1 for the censoring rules).
- Proportion of subjects without evidence of PSA or radiographic progression during the 24-month treatment period and with recovery of serum testosterone at 24 months. Testosterone recovery will be defined as a serum testosterone greater than 150 ng/dL.
- Proportion of subjects with a PSA less than 0.2 ng/mL after 7 months of protocol therapy

C) *Metabolic and Hormonal*

- Mean change from baseline in markers of insulin resistance (including body mass index, fasting glucose/insulin, and hemoglobin A1C), fasting lipid profile, and bone mineral density as measured at the femoral neck, and lumbar spine by DEXA scan over time
- Time to testosterone recovery to greater than 50 ng/dL (non-castrate) and greater than 150 ng/dL during the off-therapy observation period for subjects randomized to the LHRHa-based treatment arms (see Table 1 for the censoring rules)
- The mean change from baseline in serum DHT and estradiol levels over time

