5.3.1.2 PSA Modulation

The proportion of subjects without PSA or radiographic progression and who have recovered serum testosterone to greater than 150 ng/dL at 24 months from Day 1 will be compared for subjects treated apalutamide monotherapy vs. LHRHa monotherapy and for apalutamide + LHRHa vs. LHRHa monotherapy. The proportions by treatment will be compared using the chi-square test or Fisher's exact test as appropriate and summarized using either risk ratio or risk difference and corresponding 95% confidence interval. Results will be summarized at 24 months from Day 1 with 95% confidence intervals for each treatment arm. Subjects who withdraw from the study prior to 24 months after Day 1 will not be included and this analysis will be conducted as modified intent-to-treat (mITT).

The proportion of subjects with a PSA less than 0.2 ng/mL after 7 months of protocol therapy will be analyzed using similar approaches for proportion of subjects without evidence of PSA or radiographic progression during the 24-month treatment period and with recovery of serum testosterone at 24 months.

The probability distributions by treatment group of the time to PSA progression will be estimated using the Kaplan-Meier method. Durations will be measured from Day 1 of study treatment to the first date of PSA progression. The log-rank test will be used to compare the distribution of time to PSA progression.

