5.3.1.3 Metabolic and Hormonal Parameters

The mean change from baseline for markers of insulin resistance (including fasting glucose, insulin, body mass index, and hemoglobin A1C), fasting lipid panel (including total cholesterol, LDL, HDL, and serum triglycerides), and hormone levels (including DHT and estradiol) analyzed using a similar approach as for the primary endpoint.

The mean change in bone mineral density at the femoral neck, and lumbar spine as measured by DEXA scan will be compared for apalutamide monotherapy vs. LHRHa monotherapy and apalutamide + LHRHa vs. LHRHa monotherapy using an analysis of covariance that controls for baseline values of the corresponding measurement.

The time to serum testosterone recovery to > 50 ng/dL and > 150 ng/dL after the cessation of protocol therapy at 12 months will be compared for apalutamide + LHRHa vs. LHRHa monotherapy. The probability distributions by treatment group of the time to testosterone recovery will be estimated using the Kaplan-Meier method. The log-rank test will be used to compare the distribution of time to testosterone recovery. Subjects who discontinue study drug prior to 12 months for disease progression, unacceptable toxicity, or study withdrawal, as well as subjects who continue hormonal therapy after 12 months or receive non-protocol therapy, will not be included in the analysis of this exploratory endpoint.

No adjustment for multiple comparisons will be made for the analysis of the secondary and correlative endpoints.

Table 1: Key censoring rules

Scenario	Censoring rule
Time to PSA Progression	
 Any increase in PSA to $> 50\%$ of the baseline value or an increase of ≥ 2 ng/mL above the nadir, whichever is higher, and confirmed by repeat measurement at least 2 weeks later is considered an event. Subjects who have no PSA progression at the time of analysis will be censored at the last known date of PSA assessment. Subjects without a baseline PSA or without any post baseline values will be censored at randomization date.

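### The PSA and testosterone-recovery comparisons leave out the baseline PSA and testosterone already collected; adjusting for them would bring a modest, assumption-dependent gain

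*SAP*

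**What the plan says.** **Endpoint sections.** SAP 5.3.1.2 states for time to PSA progression: "The log-rank test will be used to compare the distribution of time to PSA progression". For the 24-month composite of no progression with testosterone recovery, "The proportions by treatment will be compared using the chi-square test", or Fisher's exact test. It then says "The proportion of subjects with a PSA less than 0.2 ng/mL after 7 months of protocol therapy will be analyzed using similar approaches" as that composite. SAP 5.3.1.3 states: "The log-rank test will be used to compare the distribution of time to testosterone recovery". None of these sentences names a covariate.

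**General section.** SAP Section 5 says "The testing for the time-to-event endpoints will be based on the stratified log rank test", with PSADT and age as strata and a stratified Cox model for the hazard ratio. It also contains this fragment, which has no verb and names no factor: "Multivariate Cox regression analysis, adjusting for important selected prognostic factors".

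**Definitions and evidence.** PSA progression is "a rise to greater than 50% of the baseline serum PSA or rise of 2 ng/mL or more above the nadir, whichever is higher", with confirmation (SAP 5.3). On testosterone, Protocol 6.4.2.3 reports from one cited study that "both older age and low baseline serum testosterone were associated with a longer time to testosterone recovery", and a second cited study points the same way, with low defined as below 212 ng/dL.

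**Data.** Day 1 PSA is the baseline for PSA endpoints (Protocol 7.3), and testosterone is drawn at screening (Protocol 7.3.2).

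**The concern.** The SAP conditions on the baseline value in its models for FACT-P, the other quality-of-life scales, the metabolic markers, DHT and estradiol, and in the bone-density ANCOVA. It does not do so for the PSA and testosterone-recovery endpoints, and gives no reason.

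For testosterone the omission sits oddly with the protocol's own argument. Protocol 6.1 makes age a stratum because it predicts recovery, and 6.4.2.3 gives baseline testosterone the same directional support. For PSA, a man's baseline affects how demanding each criterion is.

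Each pairwise comparison has about 60 men, and the results are meant to help decide whether larger trials follow. Leaving a prognostic baseline in the error costs power and exposes the comparison to chance imbalance. Leaving the Cox factors unnamed in an open-label trial also lets them be chosen after data are seen.

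**Working it through.** **Inputs.** From the documents: 30 men per arm (SAP 1.2); 27 evaluable after 10% dropout (SAP 1.4); secondary tests at two-sided 0.05 without multiplicity adjustment (SAP 5.1.1, 5.3.1.3); the thresholds in SAP 5.3; and entry minima of 1.0 ng/mL PSA after prostatectomy and 150 ng/dL testosterone (Protocol 4.2). The documents give no effect size, event rate, baseline distribution or prognostic strength for these endpoints. All of those are assumed below.

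**1. The plan's own figure.** The only sizing near this point is FACT-P superiority: 7.5 / 8.7 = 0.862, 27 per arm, two-sided 0.025. The noncentral t gives 80.2%, against the stated 80%. It does not cover the PSA or testosterone endpoints. For scale, Schoenfeld's formula at HR 0.5 and 80% power gives 4 × (1.960 + 0.842)² / (ln 0.5)² = 31.4 / 0.480 ≈ 65.4, so 66 events. That exceeds the 60 men in a pairwise comparison.

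**2. What the definitions imply.** With baseline B, the progression threshold is max(0.5B, nadir + 2). The 50% limb governs only when B > 4 + 2 × nadir. If the nadir is 5% of B (assumed), the doublings from nadir to threshold are:
- B = 1: log2(2.05 / 0.05) = 5.36
- B = 4: log2(2.2 / 0.2) = 3.46
- B = 6, 10 or 20: log2(0.5B / 0.05B) = log2(10) = 3.32

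So the gap of about two doublings lies almost wholly below 4 ng/mL, and above about 4.4 there is none. In assumed populations with median baseline 2.5 to 6, the rank correlation of baseline PSA with time to progression was -0.16 to -0.27 if nadir scales with baseline. It was +0.08 to +0.34 if nadir is unrelated to baseline.

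For PSA below 0.2, the fall needed is 1 - 0.2/B: 80% from 1 ng/mL, 95% from 4, 99% from 20. For recovery above 150 ng/dL, a man entering at 150 must exceed his whole baseline, whereas one entering at 450 needs more than 150/450, a third.

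**3. Time to PSA progression.** Simulation with 30 per arm, about 70% with events, 1,500 runs per setting, Monte Carlo error about 1 point:

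| Treatment HR | Covariate log-HR per SD | Stratified log-rank | Stratified Cox + baseline | Cox with baseline and strata as terms |
|---|---|---|---|---|
| 0.4 | 0 | 79.0% | 76.9% | 81.5% |
| 0.4 | 0.3 | 75.7% | 78.1% | 82.7% |
| 0.4 | 0.5 | 71.5% | 78.3% | 81.5% |
| 0.4 | 1.0 | 52.8% | 73.1% | 80.9% |
| 0.5 | 0 | 57.8% | 55.7% | 60.9% |
| 0.5 | 0.5 | 47.7% | 56.0% | 61.5% |
| 0.5 | 1.0 | 32.2% | 49.7% | 56.2% |

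The cleanest measure of adjustment is column four minus column three, since both keep the strata: -2.1, +2.4, +6.8 and +20.3 at HR 0.4; -2.1, +8.3 and +17.5 at HR 0.5. The last column runs higher (up to 80.9 - 52.8 = 28.1 points), but it also drops stratification, and its type I error was 5.9% to 6.5%, against 4.5% to 5.9% for the stratified log-rank. Not all of that difference is a gain from adjusting.

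**4. Testosterone recovery.** With 27 per arm, HR 0.5, and 25% of men with low baseline testosterone at log-HR -0.5 to -1.2:
- stratified log-rank: 44.0% to 37.5%
- stratified Cox + baseline: 43.8% to 40.3%, a change of about 0 to +3 points
- Cox with terms: 47.3% to 43.7%, a change of +3.3 to +6.2 points

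A further simulation of the Cox model with terms gained about 4 to 7 points when baseline was prognostic and lost essentially nothing when it was not.

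**5. PSA below 0.2 ng/mL.** Logistic likelihood-ratio tests flatter the gain. At 75% v 93% with 30 per arm, chi-square had 49% to 51% power and an *unadjusted* likelihood-ratio test 52% to 54%, so about 3 points come from changing the test. Its type I error at 90% v 90% was 7% to 9% across two simulations, against 5% to 6% for chi-square. A covariate-adjusted score test held 5% to 6% and gained 0 to 5 points. Separation is a practical risk: at a true rate of 93%, an arm of 30 has no non-responder with probability 0.93^30 = 11%.

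**The case against.** The strongest reply is that SAP Section 5 already does much of this. It stratifies the time-to-event tests by PSADT and age, both chosen for their link to these outcomes, and it mentions a multivariate Cox analysis. That is right as far as it goes. But the strata contain neither baseline, the Cox factors are not named, and the binary tests use no covariate at all.

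Second, the endpoints are exploratory and unpowered (Protocol 6.4.2.3; SAP 5.3.1.3 for recovery). For monotherapy, the hoped-for result is comparable PSA suppression rather than a difference. This stands, and it limits the weight of the point. It does not explain why a baseline already collected should go unused.

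Third, a reader might infer from the definitions that baseline PSA is a strong predictor. The documents do not show that. No passage cites such evidence, the 50% rule was chosen to individualise for baseline, and the correlations above are weak with uncertain sign. For testosterone the protocol gives a direction but no effect size.

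Fourth, a reader might conclude that the planned tests are invalid or the unadjusted hazard ratio biased. Neither follows. The log-rank and chi-square tests are valid, and the unadjusted hazard ratio estimates a marginal effect, which differs from the conditional one.

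**Conclusion.** The gap is real and modest. The three comparisons ignore a baseline that is already measured. The protocol supports its relevance for testosterone recovery; for the PSA endpoints it is plausible only.

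The change in power is about 0 to 7 points for recovery and 0 to 5 for PSA below 0.2. For time to progression it is roughly -2 to +20, where the upper end needs a strongly prognostic baseline that nothing in the documents establishes. All these figures rest on assumed effects, event rates and covariate strengths, and on the model form.

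No power is stated for these endpoints, so no stated figure is in error on this account. Nor is adjustment free in every form: a stratified Cox model could lose about 2 points if the baseline is not prognostic.

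**What to change.** - **SAP 5.3.1.3:** analyse time to testosterone recovery with a Cox model that has log baseline testosterone, age and PSADT as covariate terms, not extra strata.
- **SAP 5.3.1.2, time to PSA progression:** use a Cox model with log2(Day 1 PSA), PSADT and age as terms.
- **SAP 5.3.1.2, PSA below 0.2 ng/mL:** use a covariate-adjusted score test with a standardised risk difference, not a likelihood-ratio test. State a fallback, such as Firth or exact, for an arm with no non-responders.
- **SAP Section 5:** complete the multivariate Cox sentence by naming these factors, and align the stratified-Cox wording with the models above. Say how a missing baseline covariate is handled, since SAP 5.1.2 plans no imputation.
- **Reporting:** show the log-rank and chi-square or Fisher results alongside.
- **24-month composite:** it is tested by the same chi-square and was not simulated here. The SAP should say whether it is treated the same way.

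The cost is SAP wording and a few lines of programming, with no new data. The adjusted hazard ratios are conditional estimates, so the unadjusted ones should be shown beside them.

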5.3.1.3 Metabolic and Hormonal Parameters

The mean change from baseline for markers of insulin resistance (including fasting glucose, insulin, body mass index, and hemoglobin A1C), fasting lipid panel (including total cholesterol, LDL, HDL, and serum triglycerides), and hormone levels (including DHT and estradiol) analyzed using a similar approach as for the primary endpoint.

The mean change in bone mineral density at the femoral neck, and lumbar spine as measured by DEXA scan will be compared for apalutamide monotherapy vs. LHRHa monotherapy and apalutamide + LHRHa vs. LHRHa monotherapy using an analysis of covariance that controls for baseline values of the corresponding measurement.

The time to serum testosterone recovery to > 50 ng/dL and > 150 ng/dL after the cessation of protocol therapy at 12 months will be compared for apalutamide + LHRHa vs. LHRHa monotherapy. The probability distributions by treatment group of the time to testosterone recovery will be estimated using the Kaplan-Meier method. The log-rank test will be used to compare the distribution of time to testosterone recovery. Subjects who discontinue study drug prior to 12 months for disease progression, unacceptable toxicity, or study withdrawal, as well as subjects who continue hormonal therapy after 12 months or receive non-protocol therapy, will not be included in the analysis of this exploratory endpoint.

No adjustment for multiple comparisons will be made for the analysis of the secondary and correlative endpoints.

Table 1: Key censoring rules

Scenario	Censoring rule
Time to PSA Progression	
 Any increase in PSA to $> 50\%$ of the baseline value or an increase of ≥ 2 ng/mL above the nadir, whichever is higher, and confirmed by repeat measurement at least 2 weeks later is considered an event. Subjects who have no PSA progression at the time of analysis will be censored at the last known date of PSA assessment. Subjects without a baseline PSA or without any post baseline values will be censored at randomization date.
Time to Serum Testosterone Recovery	
 Any testosterone value between 12 months to 24 months that is greater than 150 ng/dL (or 50 ng/dL as the case may be) is considered an event. If a subject had testosterone recovery (between 12 and 24 months) that happened after hormonal or subsequent therapy started, then the subject is censored at the hormonal or subsequent therapy start date. If a subject had testosterone recovery (between 12 and 24 months) that happened before hormonal or subsequent therapy started, then the recovery is considered as an event. Subjects who were not treated will be censored at randomization date. Subjects who do not fall under any of the above-mentioned category will be censored at the end of on-therapy period or off-therapy period (if the subject is in the off-therapy period).

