Thus, in the proposed study, the proportion of subjects who completed 24 months (12 months of treatment followed by 12 months of observation) and who have recovered serum testosterone to > 150 ng/dL while remaining PSA progression and metastasis-free will be calculated as an exploratory secondary endpoint. Using a cutoff of serum testosterone greater than 150 ng/dL is acknowledged to be somewhat arbitrary, as prior clinical studies measuring the time to testosterone recovery have used a range of serum testosterone thresholds ranging from 150-300 ng/dL. Nevertheless, treatment strategies that achieve durable PSA suppression with a finite period of treatment, while either avoiding castration altogether or allowing serum testosterone recovery during Off-therapy Observation Period, would be worthy of further investigation in Phase 3 trials.

Hormone Levels: The androgen receptor is activated by various androgenic ligands besides testosterone, including dihydrotestosterone (DHT), which is produced from testosterone by the enzyme 5-alpha reductase. In hormone-sensitive prostate cancer patients treated with traditional ADT, serum levels of DHT decrease with treatment. For example, in a prior study of 69 patients treated with ADT for a period of 6 months, serum DHT levels decreased by an average of 92.5% compared with pretreatment serum levels [56]. Furthermore, bicalutamide monotherapy increases serum concentrations of testosterone and estradiol [29]. Because estradiol plays an important role in skeletal homeostasis in normal men, this may be the mechanism by which bicalutamide monotherapy lacks the adverse skeletal effects of LHRHa. A significant caveat, however, is that serum androgen levels may not reflect tissue hormone levels. Indeed, in the previously mentioned study above, though serum DHT levels decreased by 93% after 6 months of ADT, tissue DHT levels decreased by only 75%, and there was only a weak correlation between serum and tissue DHT levels ($r = 0.229$; $p = 0.025$) [57]. Nevertheless, the ready availability of serum hormone levels and their potential utility as intermediate outcome markers warrants their assessment in an exploratory fashion.

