1.4 Sample Size Justification

The expected mean decline in FACT-P score and within group standard deviation for the control arm treated with 12 months of LHRHa monotherapy are 4-8 and 8-12 points, respectively, based on prior studies of measuring QOL using FACT-P among men treated with ADT [1, 2, 3]. A change in total FACT-P score that is clinically meaningful and impacts treatment in prior studies ranges from 5-8 points depending on cancer subtype [4]. Approximately 30 subjects will be randomized to each of the 3 treatment arms for this comparison. Accounting for a dropout/questionnaire non-completion rate of 10%, this will allow for 27 evaluable subjects per study arm. For the comparison of the mean change in FACT-P score between apalutamide monotherapy and LHRHa monotherapy, this sample size has 80% power to detect an effect size of at least 0.86, corresponding to a difference of 7.5 points in mean 12 month change in FACT-P

score between treatment groups with a common standard deviation for the change in each arm of 8.7 which is similar to the reported standard deviation for LHRHa monotherapy. This is based upon a 2-group t test, using a bi-directional level of significance of 0.025 (adjusted for 2 comparisons). To test for non-inferiority in QOL with apalutamide + LHRHa compared with LHRHa monotherapy, inferior QOL is defined as a greater than 7-point difference in mean change in FACT-P score between the treatment groups and the common standard deviation is again assumed to be 8.7. This sample size has 82% power to reject the null hypothesis of a difference in mean score and accept the alternative hypothesis of non-inferiority with an effect size of at least 0.81, using a 2-group t-test with 2-sided α of 0.025.

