5.2.1 Analytic Plan for the Primary Endpoint

Change from baseline in FACT-P total scale will be analyzed using a mixed-model for repeated measures. The model will include baseline scale, treatment, month (categorical), and treatment-by-month interaction as covariates. An unstructured variance-covariance matrix will be used to model within-subject errors, but simpler structures (eg, compound symmetry) may be used to ensure estimation convergence. Change from baseline will be estimated using least-squares means with factor levels weighted according to overall baseline sample means. Data up to 12 months will be included in the analysis and the primary time point of interest will be at 12 months. Contrasts will be set up to compare apalutamide monotherapy vs. LHRHa monotherapy and apalutamide + LHRHa vs. LHRHa monotherapy. To test for non-inferiority with respect to apalutamide + LHRHa compared with LHRHa monotherapy, inferior boundary is defined as a greater than 7-point difference in mean change in FACT-P total score. The estimated least-squares mean (+/- SE) over time will be presented using a line plot. A sensitivity analysis will be conducted by including data up to 24 months.

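### DHT and estradiol: the FACT-P model, read by default as raw change with one residual covariance for all arms, gives a 95% CI too narrow for monotherapy vs LHRHa and too wide for combination vs LHRHa

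*SAP*

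**What the plan says.** SAP 5.3.1.3 handles the insulin-resistance markers, fasting lipids and hormones in one sentence, with "hormone levels (including DHT and estradiol) analyzed using a similar approach as for the primary endpoint". Protocol 11.4.2 says the same.

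The primary model (SAP 5.2.1, Protocol 11.4.1) has a single baseline term, treatment, categorical month and treatment by month. For the covariance, "An unstructured variance-covariance matrix will be used to model within-subject errors", with simpler structures allowed if the fit does not converge. SAP section 2 defines change as the post-baseline value minus the baseline value. For DHT and estradiol neither document gives a log or percentage scale, a covariance by arm, a robust standard error or a sensitivity analysis. One matrix shared by all arms is therefore the default reading. It is not stated in words, and a merely similar approach leaves some room.

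On expected hormone levels, Protocol 6.4.2.3 cites a study of 69 patients given six months of androgen deprivation in which "serum DHT levels decreased by an average of 92.5% compared with pretreatment serum levels". It adds that "bicalutamide monotherapy increases serum concentrations of testosterone and estradiol". Protocol 1.3.3 says that androgen-receptor antagonists do not bring testosterone to a castrate level. Two of the three arms receive an LHRHa and one does not.

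**The concern.** A model that pools variance over arms suits FACT-P, for which SAP 1.4 assumes a "common standard deviation for the change in each arm of 8.7". The protocol's own background makes that assumption implausible for DHT and estradiol. A hormone held at a small fraction of baseline has little absolute spread; one left at or above baseline has much more. The pooled variance then lies between the two. It understates the error of any contrast that includes the monotherapy arm and overstates the error of the contrast between the two castrated arms.

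Mean change in DHT and estradiol is a listed secondary endpoint (SAP 5.3), and both pairwise comparisons of hormonal effects are a stated objective (SAP 1.1.2). SAP 5.1.1 promises two-sided 95% intervals, and these would not have that coverage.

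**Working it through.** **The plan's own figure.** The documents give no precision or power for the hormones. The only power calculation of this type is for FACT-P superiority, where "this sample size has 80% power to detect an effect size of at least 0.86". Inputs: difference 7.5, SD 8.7, 27 evaluable per arm, two-sided 0.025. Effect size = 7.5/8.7 = 0.862; 27/(1 − 0.10) = 30 randomised per arm; power by noncentral t = 80.2%. It reproduces, and it rests on equal SDs across arms.

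**Direction, in closed form.** Take three equal arms of size n, with residual SD s in each castrated arm and k·s in the monotherapy arm.
- Pooled variance = (2 + k²)s²/3, so both contrasts get model variance 2(2 + k²)s²/(3n).
- True variance is (1 + k²)s²/n for monotherapy vs LHRHa and 2s²/n for combination vs LHRHa.
- Model SE / true SE is therefore √[2(2 + k²)/(3(1 + k²))] and √[(2 + k²)/3].

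| k | Mono vs LHRHa: SE ratio (coverage) | Combination vs LHRHa: SE ratio (coverage) |
|---|---|---|
| 1 | 1.00 | 1.00 |
| 2 | √(12/15) = 0.89 (92.5%) | √(6/3) = 1.41 (99.5%) |
| 3 | √(22/30) = 0.86 (91.2%) | √(11/3) = 1.91 (99.99%) |
| 5 | √(54/78) = 0.83 (90.2%) | √(27/3) = 3.00 (about 100%) |

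The first ratio cannot fall below √(2/3) = 0.816. The second has no upper limit.

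**Size, by simulation.** The simulation used 20,000 trials with 27 per arm. Each was a three-arm ANCOVA of raw change at one visit, with a common baseline slope and pooled variance, standing in for the complete-data month-12 contrast. From the protocol: castrate DHT ratio 1 − 0.925 = 0.075. Assumed: DHT ratio on monotherapy 1.0–1.5, estradiol ratio 0.2–0.4 in castrated arms and 1.3–2.0 on monotherapy, CVs 30–50%.

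| Marker | Mono vs LHRHa: SE ratio, coverage | Combination vs LHRHa: SE ratio, coverage |
|---|---|---|
| DHT | 0.83–0.86, 86–88% | 1.7–3.1, 99.8–100% |
| Estradiol | 0.84–0.87, 88–90% | 1.7–2.2, 99.8–100% |

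The residual SD ratio k ran from about 2.6 to 5.1 in these scenarios, so the results agree with the closed form. Coverage for monotherapy vs LHRHa is somewhat lower than the closed form gives because the data are skewed.

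The common slope contributes too. If on-treatment level is proportional to baseline, the slope of change on baseline is 0.075 − 1 = −0.925 in the castrated arms and 1.0 − 1 = 0 on monotherapy at ratio 1.0. The pooled slope of (2 × −0.925 + 0)/3 = −0.617 fits neither. This leaves extra residual error in the castrated arms and so keeps k lower than it would otherwise be.

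**Power for combination vs LHRHa.** Assume baseline CV 40%, log SD 0.35, and a combination that lowers DHT a further 30%. Power is about 0.1% on the raw scale and 96% on the log scale. With assumed estradiol ratios of 0.30, 0.21 and 1.5 (LHRHa, combination, monotherapy), it is 1.8% and 96%.

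**Alternatives.** Log ratio with pooled variance: SE ratio 0.93–1.09 and coverage 93–97% for both contrasts. Raw change with arm-specific variances: coverage about 91–94% for monotherapy vs LHRHa and 95–96% for combination vs LHRHa.

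**The case against.** **The harm to conclusions is limited.** This stands in part. Under these inputs monotherapy and LHRHa differ in DHT by about 92.5% of baseline. In 4,000 simulated trials the median raw-scale t was 12.6 and the smallest 5.5. A reader might infer that the narrow interval threatens a false claim for monotherapy. It does not; only the stated precision is wrong. For combination vs LHRHa the error is conservative and creates no false positives.

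**No further hormone fall on the combination is proposed.** This stands. The documents describe ARN-509 as a receptor antagonist, not as a DHT-lowering drug. A further 30% of the remaining 7.5% is 2.25% of baseline. The power figures show what the analysis could detect if such a difference existed; they do not predict one.

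**Insulin and triglycerides sit in the same sentence of the SAP.** A reader might infer that they share the fault. The documents give no reason to expect castration to change their spread as it does for DHT. With the same skewed multiplicative error in all arms (assumed CV 40–70%, castrated-arm level 1.0–1.5 times baseline), coverage stayed at 93–96% for both contrasts. If castration raises these markers, the pattern reverses slightly. For them a log scale is only a choice about skewness and efficiency.

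**The log scale has its own weakness.** This stands. Castrate DHT may lie near the assay limit, which the documents do not give. With an assumed limit at the mean castrate level and half-limit substitution, log-scale coverage for monotherapy vs LHRHa fell to 78% (74% with the further 30% fall), and power for combination vs LHRHa fell from 96% to 68%.

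**Readers will see the unequal spread.** SAP section 5 does report SD, median and range, but that does not correct the intervals.

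**Conclusion.** The point holds for DHT and estradiol. If the primary model is applied as it would normally be read, the nominal 95% interval is about 13–17% too narrow for one planned contrast and about 1.7–3 times too wide for the other. The direction needs only unequal SDs, which the protocol's background makes foreseeable. The size rests on assumed CVs and monotherapy ratios; only the 92.5% DHT fall comes from the documents, from a cited study of earlier patients. The protocol gives no size for the estradiol rise and nothing on DHT under receptor-antagonist monotherapy.

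The shared covariance is inferred from silence. If the sponsor already intends an arm-specific matrix, most of the problem goes and the SAP need only say so. Protocol 6.4.2.3 calls the hormone measures exploratory, and SAP 5.3.1.3 applies no multiplicity adjustment. The correction is worth making because it is cheap and these results are meant to inform later trials.

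**What to change.** In SAP 5.3.1.3, for DHT and estradiol:

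1. Analyse the log ratio to baseline with log baseline as covariate, otherwise with the same repeated-measures terms, and report geometric mean ratios with 95% CIs for both contrasts.
2. State before database lock how values below the assay limit are handled, and report their number by arm and visit.
3. Keep the mean raw change listed in SAP 5.3, but fit it with a residual covariance by arm, or with robust standard errors, and show it beside the log analysis because the latter is sensitive to below-limit values.

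No change to insulin or triglycerides is needed on this ground.

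The cost is SAP wording and a small change to the code; no new data are needed. Log-scale results read as ratios rather than units. A separate unstructured matrix per arm over the four on-therapy visits (Months 3, 6, 9 and 12) has 4 × 5/2 = 10 parameters per arm, 30 in all, from about 27 subjects per arm. The SAP should therefore say that its fallback to a simpler structure also applies by arm.
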